6.5.2 Prohibited Medicines

Administration of any investigational product or use of any investigational device within 30 days prior to first administration of the IMP and during the entire clinical trial is not permitted.

No medication from screening until the last PK sample is allowed without prior approval from the Investigator (except for occasional use of paracetamol or ibuprofen). Attention should be paid to any drugs that may affect CYP450 enzyme status, e.g. phenytoin, barbiturates, primidone, carbamazepine, oxcarbazepine, topiramate, felbamate, rifampicin, nelfinavir, ritonavir, griseofulvin and oral ketoconazole.

Subjects who two weeks prior to dosing have consumed substances known to be potent inhibitors or inducers of CYP P450s such as grapefruit, orange, cranberry or juices of these fruits, herbal remedies or dietary supplements containing St. John's Wort, poppy seeds, cruciferous vegetables are not allowed to participate in the study.

If the administration of a non-permitted concomitant drug becomes necessary during the trial, e.g. because of AEs, the subject should be discontinued from the trial but only after consultation with the Sponsor.

6.5.3 Other Interventions

Subjects who have been exposed to agents known as inducers or inhibitors of liver enzymatic systems, who have taken drugs potentially toxic within 30 days prior to the study start-up, who require any drug throughout the study, who have history of gastrointestinal tract surgery which might affect gastrointestinal absorption and/or motility are not allowed to participate in the study.

6.5.4 Special Precautions

Subjects who have excessive consumption of beverages containing xanthine (>5 cups of coffee a day or equivalent) or inability to stop consuming caffeine from 48 hours prior to drug administration until discharge from the clinic are not allowed to participate in the study.

Subjects who have history or presence of drug abuse (opiate class, barbiturates, cocaine and its main metabolite, amphetamines, cannabinoids, benzodiazepines and tricyclic antidepressants) or alcohol abuse at screening and on each admission are not allowed to participate in the study.

Standardization of Physical Activity

While resident in the trial site, the subjects will be confined to bed during the first 1 hour after the IMP administration. Thereafter, they may get out of bed, however restricting their activity to a minimum. Subjects should avoid excessive physical exercise throughout the trial until collection of the last PK sample.

Smoking Restrictions

Only non-smoking subjects or subjects who have refrained from smoking for at least 3 months prior to Screening.

In case of adverse events, medical staff will provide medical care required depending on the adverse event occurred. In case of severe eventuality, which requires hospital admission, the Principal Investigator or medical staff on duty will request the transfer of the subject to the agreed hospital and will contact the external ambulance service, according to the standard operating procedure, code: IC-PNO-033, Management of Clinical Eventualities.

6.5.5 Management of Specific Adverse Events or Adverse Drug Reactions

In case of adverse events, medical staff will provide immediate medical care required depending on the adverse event occurred. The Principal Investigator will decide the subsequent management, according to the standard operating procedure, code: PPD [redacted], Management of Clinical Eventualities.

6.6 Packaging and Labeling of the Investigational Medicinal Product

Cisticid® Merck, Mexico S. A. de C. V.

CCI [redacted]

[redacted]

Test product will be given orally as a single dose of 1200 mg (two tablets) of Cisticid with 250 mL of water during a breakfast.

Biltricide Bayer HealthCare Pharmaceuticals Inc.

CCI [redacted]

CCI

Reference product will be given orally as a single dose of 1200 mg (two tablets) of Praziquantel, given with 250 mL of water during a breakfast.

All IMPs will be packaged and labeled in accordance with all applicable regulatory requirements and Good Manufacturing Practice Guidelines.

6.7 Preparation, Handling, and Storage of the Investigational Medicinal Product

IMPs will be received at the PPD [redacted], S. C. by the Pharmacy Responsible or by the designated staff, as per the standard operating procedures, code: PPD [redacted]: Receipt, use, balance and final disposition of the study drug. Once drugs have been identified, they will be kept by the clinical unit until they are administered to the subjects.

Acceptance criteria for test and reference drugs:

- Complete documentation:
 - Certificate of Analysis.
 - Dosage units.
 - Content assessment.
 - For test drug, letter of Good Manufacturing Practice compliance.
 - For reference drug, confirmation from Bayer that material was donated and belongs to a batch that has been released as commercial material.
 - For reference drug, copy of the zero-charge invoice from the packaging site (Merck Spittal).
- Test drug with label compliant with the minimum requirements from NOM-072-SSA1-2012, Labelling of Drugs and Herbal Remedies (25).
- Enough quantity of test and reference drug for the trial and for retention medication.
- Expiry date not due at the moment of use in the clinical study.
- Test and reference drug in good physical conditions.

Rejection criteria for test and reference drugs:

- Evidence of tampering of primary packaging.

- Drug received out of the storage or transportation specifications.
- Evidence of damage to primary packaging (physical damage from any source e.g. impact, moisture, insects and rodents, etc.)

CCI

6.8 Investigational Medicinal Product Accountability

The Principal Investigator, Pharmacy Responsible or designated staff at the PPD , S. C. will be in charge for ensuring IMP accountability, including reconciliation of drugs and maintenance of records, according to the standard operating procedure, code: PPD : Preparation and administration of drugs in clinical trials of interchangeability and PPD : receipt, use, balance and final disposition of the study drug.

- Upon receipt of IMP, the responsible person will check for accurate delivery and acknowledge receipt by signing or initialing and dating the appropriate documentation and returning it to the location specified. A copy will be archived for the Investigator Site File.
- IMP dispensing will be recorded on the appropriate drug accountability forms so that accurate records will be available for verification at each monitoring visit.
- Trial site IMP accountability records will include the following:
 - Confirmation of IMP receipt, in good condition and in the defined temperature range.
 - The inventory of IMP provided for the clinical trial and prepared at the site.
 - The use of each dose by each subject.
 - The disposition (including return, if applicable) of any unused IMP.
 - Dates, quantities, batch numbers, vial numbers, expiry dates, formulation (for IMP prepared at the site), and the individual subject trial numbers.

The Pharmacy Responsible site should maintain records, which adequately document that subjects were provided the doses specified in this protocol, and all IMPs provided were fully reconciled.

Unused IMP must not be discarded or used for any purpose other than the present trial.

A Trial Monitor will periodically collect the IMP accountability forms according to the standard operating procedure, code: PPD [REDACTED] Receipt, use, balance and final disposition of the study drug.

The Sponsor will ship enough quantities of the test and reference product to conduct the study and keep enough as "retention samples" to the Clínica de PPD [REDACTED]

6.9 Assessment of Investigational Medicinal Product Compliance

Throughout dosing period, dose, full intake and time will be checked and recorded in the appropriate forms and CRF, according to the standard operating procedure, code: PPD [REDACTED] : Preparation and administration of drugs in clinical trials of interchangeability and biocomparability; PPD [REDACTED], randomization in an interchangeability and biocomparability clinical study

A subject is compliant with the treatment only if he completes all study periods.

6.10 Blinding

Not applicable, this is an open-label trial for subjects but analysts will be blinded.

6.11 Emergency Unblinding

Not applicable, this is an open-label trial.

6.12 Treatment of Overdose

Overdose is defined as any dose higher than the highest daily dose included in the clinical protocol or foreseen for a subject recruited in the study. Even though this does not meet criteria for serious adverse event, any overdose should be recorded in the study drug section of the CRF and medical chart.

It should be reported to the *National Center of Pharmacovigilance* (CNFV) from the *Federal Commission for the Protection Against Sanitary Risks* (PPD [REDACTED]), according to the standard operating procedures, code: PPD [REDACTED], Adverse event reporting in clinical and bioavailability studies and the Mexican Official Standard for Setting-up and Operations of Pharmacovigilance in Mexico, PPD [REDACTED] (29) and following procedure listed in section 7.4.1.9.

Information on overdose of PZQ in humans is not available. Treatment should be supportive and provide symptomatic care.

6.13 Medical Care of Subjects after End of Trial

Subjects will sign a consent, which states that they will receive an economical compensation for their participation in the study. The Sponsor will pay treatment (or compensation, if applicable) resulting from injuries or diseases caused by their participation in the study until their resolution as per the clinical criteria. The Sponsor will not pay injuries caused by subject's negligence, irresponsible behavior or medical reasons no related to the study.

External follow-up will be given to all subjects recruited in the study. As per the last dose of the drug, free appointment or telephone contact will be available as per the Principal Investigator's judgment, for a period equivalent to the established wash-out period.

7 Trial Procedures and Assessments

At the beginning of each period, on day -1 and one hour prior to initial dosing, a physical examination will be done (including general appearance, skin, head, neck (including thyroid), ears, nose, throat, cardiovascular and pulmonary system, abdomen, neurological, peripheral vascular, and musculoskeletal system, oral cavity examination) as well as vital signs measurement, ECG and follow-up of adverse events. Blood and urine samples will be taken (day -1 only, following a 10-h fasting period) for safety laboratory tests such as hematology; blood chemistry, and urinalysis as well as urine sample for drug screening and alcohol breath test will also be performed in order to check if the subject remains eligible for the study.

Subjects should inform the medical staff in charge of the study conduct about any symptom they might have. Likewise, medical staff will question the subjects in every study period about symptoms occurred since recruitment in the first period, prior and following dosing. In case they report any, they will be provided with care and notes will made in the appropriate documents.

During each period, the vital signs (3, 7, 11h post dose) and the PK samples (see [Table 4](#)) will be taken.

During each period, safety laboratories test will be performed such as hematology, blood chemistry and urinalysis. Samples will be taken pre-dose (day -1 only, following a 10-h fasting period) and at discharge (24 h post-dose).

At the end of each period, at discharge (24 h post-dose) a clinical assessment consisting of an interview, physical examination (including general appearance, skin, head, neck (including thyroid), ears, nose, throat, cardiovascular and pulmonary system, abdomen, neurological, peripheral vascular, and musculoskeletal system, oral cavity examination), vital signs measurement, ECG and follow-up of adverse events, will be done. Blood and urine samples will be taken for safety laboratory tests such as hematology; blood chemistry, and urinalysis.

At the last visit a clinical assessment consisting of an interview, physical examination (see above) will be performed. Weight, ECG, vital signs and adverse events follow-up will be carried out. Blood and urine samples will be taken for safety laboratory tests such as hematology; blood

chemistry, and urinalysis, this visit will be performed around seven days after the last administration of the IMP, day 22.

Due to operational issues, the Principal Investigator may modify start of the study (starting as per the dosing of study drug) for one hour, as long as there is no impact on the study results.

7.1 Schedule of Assessments

Detailed schedule of study procedures/assessments is provided in Section 12.2 Appendix 2 Schedule of Assessments.

Prior to performing any trial assessments, the Investigator will obtain written informed consent as described in Section 9.2

In case of several assessments planned at the same time point, the PK samples will be taken at the predefined time point. The ECG recordings, followed by vital signs measurements, will be performed before PK sampling. Any ECG and vital signs taken within 60 minutes predose will be considered to have been taken at the scheduled time point. Safety laboratory samples collected within 15 minutes of the scheduled time point will be considered to have been taken at the scheduled time point. Sampling for safety laboratory will be assessed after PK blood sampling. All actual times need to be recorded in the eCRF.

The allowed deviation from the prespecified assessment time will be:

Predose samples:

- Within 1 hour before IMP administration

Postdose samples and assessments:

- Up to and including 24 hours: $\pm 5\%$ of scheduled time point in minutes
- After 24 hours up to and including 96 hours: ± 1 hour
- After 96 hours: ± 4 hours

7.1.1 Screening of Subjects

Screening of the subjects will take place within 28 days prior to the first administration of the trial medication, according to the standard operating procedures, code: PPD Recruitment subjects, and comprises the following:

- Informed consent for participation in the trial,
- Inclusion/exclusion criteria checked.
- Demographics including body height and body weight and BMI, nicotine consumption, smoking history, alcohol consumption, intake of caffeine or xanthine-containing beverages, intake of grapefruit, orange, cranberry or juices of these three fruits and other things as described in Section 6.5.2)

- Medical history and history of medications
- Vital signs (body temperature, as well as blood pressure (BP) and pulse rate after at least 5 minutes rest in supine position),
- Physical examination
- Safety laboratory: biochemistry tests, hematological tests, urinalysis and Serology test,
- An urine drug screen test,
- 12-lead standard ECG (after 5 minutes rest in supine position),

Concomitant medications, AEs and procedures will be continuously assessed from signature of informed consent to the end-of-trial examination.

If no clinically relevant finding is made at screening and the subject satisfies all of the protocol inclusion criteria and none of the exclusion criteria, the subject will be considered as eligible and will be enrolled into the clinical trial.

Subjects who fail to meet the protocol specified criteria for dosing or who withdraw their consent in the screening period are considered screening failures. The following data will be recorded for these subjects: demographics (including age, weight and height), AEs, concomitant medications and reason for screening failure.

7.1.2 Treatment periods 1, 2, and 3

Day -1/7/14:

- Admission the day prior to the visit for assuring 10-h fasting period.
- Blood and urine samples will be taken (day -1 only, following a 10-h fasting period) for safety laboratory tests such as hematology; blood chemistry, and urinalysis
- Subject's eligibility will be checked again
- Dinner at least 10 h before the dosing.

Day 1/ 8 / 15:

- At 5:00 h, grooming and intake of 250 mL of water.
- Between 05:20 and 06:30 h, electrocardiogram will be performed.
- Post electrocardiogram the following activities will be done:
 - Catheter insertion (pre-dose sample).
 - Vital signs will be measured at 3, 7, and 11 h after dosing.
 - Adverse events and previous medication

- Randomization for the first period of treatment only
- At 07:30 h, breakfast. They will be given 20 minutes as maximum for having food, time should be recorded.
- At 08:00 h, oral administration of IMP with 250 mL of water at room temperature p.o., according to the standard operating procedure, code: BE-PNO-012: Preparation and administration of drugs in interchangeability and biocomparability clinical studies.
- From 08:15 to 20:00 h, PK sampling as per the schedule of assessments.
- At 11:00 h, 250 mL of water
- At 13:00 h, light lunch
- As from 16:00 h, lunch.
- As from 21:00 h, dinner.

Day 2/ 9 / 16:

- At 07:00 h, electrocardiogram will be performed.
- At 08:00 h, safety laboratory tests (hematology, blood chemistry and urinalysis) and catheter removal.
- At 08:30 h, vital signs will be measured
- Physical examination.
- Approximately at 10:00 h, discharge (temporarily on Day 2 and 9) from the clinical unit.

7.1.3 End of Trial (EoT)

- Physical examination and weight measurement for each subject.
- Vital signs measurement.
- Electrocardiogram.
- Safety laboratory tests (hematology, blood chemistry and urinalysis)

Prior to performing any trial assessments that are not part of routine medical care for the subject, the Investigator will obtain written informed consent as described in Section 9.2.

7.2 Demographic and Other Baseline Characteristics

At screening (within 28 days before first administration), the following demographic data will be collected: date of birth, sex (gender), race and ethnicity. Specify any additional critical variables to be assessed such as:

- Information about previous and concomitant medications, medical history data including medication history within the last 5 years consisting of all previous diseases as considered relevant by the Investigator and all previous hospital stays, previous medication consisting of all previous medications within the last 5 years as considered relevant by the Investigator, and all regularly taken medications within the last year,
- No efficacy in this study Weight, height and BMI
- Special diets
- Month prior to drug administration, nicotine consumption
- Smoking history
- Alcohol consumption
- Consumption of caffeine or xanthine-containing beverages, intake of grapefruit, orange, cranberry or juices of these three fruits, intake of food containing xanthine and usual diet, physical examination, and serum virology
- Safety laboratory
- ECG
- Vital signs

7.3 Efficacy Assessments

Not applicable.

7.4 Assessment of Safety

The safety profile of the IMP will be assessed through the recording, reporting and analyzing of baseline medical conditions, adverse events (AEs), physical examination findings including vital signs (body temperature, blood pressure, and pulse rate), 12-lead electrocardiogram (ECG), and laboratory tests (hematology, biochemistry, urinalysis, and coagulation).

Comprehensive assessment of any apparent toxicity experienced by each subject will be performed from the time of giving informed consent and throughout the trial. The Investigator will report any AEs, whether observed by the Investigator or reported by the subject (see Section 7.4.1.7). The reporting period for AEs is described in Section 7.4.1.8.

7.4.1 Adverse Events

7.4.1.1 Adverse Event Definitions

Adverse Event

An adverse event (AE) is any untoward medical occurrence in a subject or clinical investigation of the subject administered a pharmaceutical product which does not necessarily have a causal relationship with the study drug. Therefore, an adverse event can be any unfavorable and unintended sign (including any abnormal laboratory finding), symptom or condition/disease temporarily associated with the use of the investigational drug, whether or not considered related to that product.

In cases of surgical or diagnostic procedures, the condition/illness leading to such a procedure is considered as the AE rather than the procedure itself.

7.4.1.2 Adverse Event's Causality with the Investigational Product

Investigators must systematically assess the causal relationship of AEs to IMP(s) using the following definitions. Decisive factors for the assessment of causal relationship of an AE to the IMP include, but may not be limited to, temporal relationship between the AE and the IMP, known side effects of IMP, medical history, concomitant medication, trial procedures.

Causality will be assessed using both NOM-220-SA1-2016 (29) and Merck standard. Adverse event records and reporting by PPD should include causality assessment per both the NOM and Merck standard scale described above as follows:

Per Merck standard:

Unrelated: Not reasonably related to the IMP/study treatment. AE could not medically (pharmacologically/clinically) be attributed to the IMP/study treatment under study in this clinical trial protocol. A reasonable alternative explanation must be available.

Related: Reasonably related to the IMP/study treatment. AE could medically (pharmacologically/clinically) be attributed to the IMP/study treatment under study in this clinical trial protocol.

Per the regulation in Mexico, NOM-220-SA1-2016 (29):

Certain. It consists of an event (clinical onset or an abnormal result of laboratory test) which occurs within a reasonable period of time following the drug's administration and which cannot be explained by the natural condition's evolution, by any concomitant pathology or by other drugs dosing. Response to drug's stop should be clearly evident.

Probable. It consists of an event (clinical onset or an abnormal result of laboratory test) which follows a reasonable period of time following the drug's administration and which can hardly be related to the natural condition's evolution, concomitant pathologies or to other drugs dosing. A clinically reasonable response is obtained upon stop of other(s) drug(s).

Possible. It consists of an event (clinical onset or an abnormal result of laboratory test) which follows a reasonable period of time following the drug's administration and which can hardly be related to the natural condition's evolution, concomitant pathologies or to other drugs dosing. There is no information available related to the suspect drug's dosing or this is not clear.

Suspect. It consists of an event (clinical onset or abnormal laboratory test) which follows a reasonable sequence of time following the drug's dosing which makes causality unlikely (but not impossible). It might be explained in a reasonable way since it is part of the natural evolution of the condition, or it is due to the presence of concomitant pathologies or other drugs dosing.

Conditional - Unclassifiable It consists of an event (clinical onset or abnormal laboratory test result) which cannot be properly assessed since more data are required or because additional data are still being analyzed.

Not evaluable - Unclassifiable It consists of a report which suggest that there is an adverse reaction which cannot be assessed since collected information is not enough or inconsistent. The report cannot be completed or checked

Other factors to be considered for adverse event's causality assessment with the study drug are:

- ✚ Recovery or discontinuation, relapse or rechallenge: Subject's response following stopping the drug or subject's response following rechallenge should be considered based on the usual clinical course of the corresponding event.
- ✚ Response pattern known for this type of drug: Clinical/Pre-clinical
- ✚ Exposure to physical and/or mental stress: Exposure to stress may produce adverse changes in the receptor and provide a rationale and a better explanation for the event.

Test drug's pharmacology and pharmacokinetics: Test drug's pharmacokinetic properties (absorption, distribution, metabolism and excretion) as well as the subject's individual pharmacodynamics should be considered.

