7.4.1.11 Monitoring of Subjects with Adverse Events

Adverse events are recorded and assessed on an ongoing basis throughout the study, and they will be assessed for the final outcome in the 7 day follow-up following the last dose of the drug.

Any AE that occurs during the course of a clinical trial and is considered to be possibly related to the IMP must be monitored and followed-up by the Investigator until stabilization or until the outcome is known, unless the subject is documented as "lost to follow-up". All reasonable efforts should be made to collect information and these should be documented. It is also the Investigator responsibility to ensure that all additional and necessary therapeutic measures are taken as well as the follow-up procedures.

The outcome of an adverse event should be entered in the eCRF, with the terms provided below:

- Recovered without sequelae;
- Recovered with sequelae;
- Ongoing;
- Worsening;
- Improving;
- Died;
- Unknown.

In case of a fatality, the cause of death is considered as the SAE, and the death is considered as its outcome.

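### In Protocol 7.4.1.2 the Probable definition contradicts itself and Possible repeats its alternative-cause condition, so ratings on the Mexican-standard causality scale can be inconsistent or wrong

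*Protocol*

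**What the plan says.** Protocol 7.4.1.2 requires causality to be assessed on two scales, both of which go into adverse event records and reports. One is the sponsor's binary Related/Unrelated scale. The other is a graded scale attributed to the Mexican pharmacovigilance standard.

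On the graded scale:

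- Certain describes an event "which cannot be explained by the natural condition's evolution, by any concomitant pathology or by other drugs dosing", and adds "Response to drug's stop should be clearly evident".
- Probable describes an event that "can hardly be related to the natural condition's evolution, concomitant pathologies or to other drugs dosing", and adds "A clinically reasonable response is obtained upon stop of other(s) drug(s".
- Possible uses the same alternative-cause clause as Probable, and adds "There is no information available related to the suspect drug's dosing or this is not clear".
- Suspect covers an event whose timing is said to be of a kind "which makes causality unlikely (but not impossible", and which has a reasonable alternative explanation.
- Two unclassifiable categories cover reports with missing, pending or inconsistent information.

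The section then lists further factors for the assessor. On withdrawal of drug it says: "Subject's response following stopping the drug or subject's response following rechallenge should be considered".

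Two later sections use the causality rating. Protocol 7.4.1.11 says that an event that "is considered to be possibly related to the IMP must be monitored and followed-up by the Investigator" until it stabilizes or its outcome is known. Protocol 8.4.4.1 has adverse events analyzed by relationship to trial drug. Neither names a scale or a category. SAP section 18 only refers to the clinical report.

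**The concern.** Investigators are told to rate causality with these definitions, so the wording is operative. Three things look wrong.

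1. The response clause in Probable names the wrong drug. If an event resolves when another drug is stopped, that is evidence for the other drug and against the investigational product.
2. Possible sets the same bar on alternative causes as Probable. A graded scale would be expected to relax that bar from one step to the next.
3. As a result, an event with two plausible causes has nowhere to go except a category that calls causality unlikely.

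At stake are the consistency of the graded ratings, the relationship tables if they were built on this scale, and the follow-up trigger in 7.4.1.11 if it is read through this scale. Safety and tolerability of the new tablet is a secondary objective (Protocol 4.2). The primary bioequivalence analysis uses no causality rating.

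**Working it through.** No arithmetic applies, because the documents give no figure that depends on these definitions. The check is a comparison of the texts.

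**Step 1: set the categories side by side.**

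| Category | Condition on other causes | Further condition |
|---|---|---|
| Certain | Cannot explain the event | Clear response to stopping the drug |
| Probable | Hardly explain the event | Response to stopping other drugs |
| Possible | Hardly explain the event (same words as Probable) | Information on the suspect drug's dosing absent or unclear |
| Suspect | Reasonably explain the event | Causality called unlikely but not impossible |

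**Step 2: test Probable against itself and its neighbours.** The first half makes other drugs an unlikely cause. The second half relies on improvement when other drugs are stopped. An event that met the second half would be evidence against the first. Certain, and the general factor on stopping the drug, both refer to the drug under assessment. Probable is the only place that refers to other drugs.

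**Step 3: test Possible against Probable.** The alternative-cause clause is identical, so only the last sentence separates the two. Read literally, that sentence requires the suspect drug's dosing to be unknown or unclear. In this trial that should be rare: doses are given at the clinic with a mouth check (Protocol 6.2), and dose, full intake and time are checked and recorded (Protocol 6.9).

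**Step 4: place an event with a competing cause.** Take a headache after dosing in a subject who has stopped caffeine, as Protocol 6.2 requires from 48 hours before dosing. The timing fits the product, and caffeine withdrawal is a reasonable alternative.

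- Certain fails, because another cause can explain the event.
- If caffeine withdrawal is counted among the alternative causes that the scale lists, Probable and Possible fail too, because the event can readily be put down to something else.
- The unclassifiable categories do not fit, because the information is complete.
- Suspect is what remains, and it labels causality unlikely.

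**Step 5: trace the consequences.**

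- *Follow-up.* The trigger in 7.4.1.11 is an event possibly related to the product. The graded scale is the only one of the two with a category called Possible. If a site reads the trigger as Possible or higher, events rated Suspect fall outside it. If the site reads the words in their ordinary sense, Suspect events can fall inside it, since causality there is not impossible.
- *Tables.* Section 8.4.4.1 does not say which scale defines relationship. If the graded scale were used, the tables would inherit the problem. If the sponsor's scale were used, they would not.

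**The case against.** The strongest case on the other side has five parts.

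**The sponsor's scale is sound and runs in parallel.** Related covers an event that could medically be attributed to the product. Unrelated requires that it could not, and that a reasonable alternative exists. An event with two plausible causes is therefore captured as Related. This stands, and it confines the defect to the graded scale and to whatever is read through it.

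**The literal clauses will seldom be tested.** Subjects are healthy, other medication needs investigator approval apart from occasional paracetamol or ibuprofen (Protocol 6.5.2), and treatment is by single doses, so stopping a drug has limited application. This stands as a limit on size. It also means that the clauses meant to separate the categories give the assessor little help here.

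**The follow-up rule names no scale.** Section 7.4.1.11 also has all events assessed for final outcome at the 7-day follow-up, and Protocol 6.13 provides external follow-up for all subjects. This stands. Loss of follow-up is a possibility under one reading, and not a stated consequence.

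**Possible does not exclude other causes.** A reader might infer that it requires them to be ruled out. The text says only that they can hardly account for the event. Only Certain excludes them.

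**The cited standard is not available here.** The documents show that Probable and Possible share a clause. They cannot show that this departs from the standard, so the correct wording of Possible cannot be dictated from them. The contradiction inside Probable needs no outside source.

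**Conclusion.** The point holds as a minor error in definitions. Probable contradicts itself, Certain and the general factor on stopping the drug. Possible duplicates the alternative-cause condition of Probable. An event with plausible timing and a reasonable competing explanation is left with Suspect. Ratings on the Mexican-standard scale can therefore be inconsistent, or wrong if the text is followed literally. The effect on follow-up depends on reading the trigger in 7.4.1.11 as Possible or higher. The sponsor's Related/Unrelated scale and the bioequivalence conclusion are unaffected.

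Three stronger conclusions are tempting, and the documents do not support them.

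- A reader might infer that event relationships *are* misassigned. The text shows a risk on one of two scales, with no evidence of how sites applied it.
- A reader might infer that related events are undercounted. The two defects pull in opposite directions: crediting the product when another drug is stopped would inflate the count, and sending mixed-cause events to Suspect would lower it. The net direction is not established.
- A reader might size the problem by applying the common frequencies in Protocol Table 1 to the planned doses. That would count all events rated, not those whose rating would change. The protocol also notes that some listed reactions may come from the killing of parasites, so the frequencies may not carry over to healthy volunteers.

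**What to change.** In Protocol 7.4.1.2:

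- Reconcile the response clause in Probable with the general factor on stopping the drug in the same section.
- Check the wording of Probable and Possible against the cited Mexican standard, and correct either one where it departs.

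In Protocol 7.4.1.11, state which scale and which categories count as possibly related for follow-up.

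In Protocol 8.4.4.1, state which scale defines relationship to trial drug. The Related/Unrelated scale is the natural choice for the tables, because it is free of the defect and required in the adverse event records.

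The cost is a few sentences of wording and a short note to the site. No analysis, sample size or data collection changes.
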